Cover Page:

The Effects of Dexamethasone on the Time to Pain Resolution in Dental Periapical Abscess

NCT03005522

Document. Date: 12/01/2020

Study Protocol

MATERIALS AND METHODS

A prospective, randomized, double-blind placebocontrolled study was undertaken at two academic medical center EDs between September 2017 and May 2019. All patients presenting with "dental pain" were screened for potential study enrollment. Patients 18 years and older with a clinical diagnosis of pulpitis or dental apical abscess were further screened for potential enrollment. Diagnosis was made based on physical examination revealing pain with percussion of the affected tooth or teeth with or without gingival erythema or swelling.

Patients were excluded for any of the following conditions: diabetes, treatment with systemic corticosteroids within the last 30 days, hospitalization due to intractable vomiting or pain, self-reported pregnancy, immunosuppression (diagnosed with human immunodeficiency virus, received transplantation, or receiving chemotherapy), or those who lacked a telephone number to participate in follow-up calls. Eligible patients were approached for potential study inclusion and, after providing informed consent, enrolled patients were randomized to receive either dexamethasone 10 mg or an identical placebo.

Study drug, placebo, and two separate randomization lists were prepared for each study site by the investigational drug pharmacist. Randomization was achieved by using a random number generator of blocks of four to maintain relatively equal group sizes. The study drug was prepared using capsules filled with either sucralose granules or crushed dexamethasone tablets. Four 2.5-mg tablets were crushed and mixed with sucralose granules for each active study drug preparation. Study drug and placebo were prepared using identical capsules to maintain blinding. The investigators, patients, and treating provider remained blinded. Only the investigational drug pharmacist, who was not involved in the care of these patients, had the ability to unblind the study if necessary for patient safety.

Medical management of each patient was performed at the discretion of the treating provider. Data on therapeutic modalities, including the use of local anesthetic blocks, analgesics, and antibiotics, were gathered for each patient to allow for comparison between the dexamethasone and placebo groups. Termination from study enrollment occurred if the patient required dental extraction or pulpectomy during the 72-h follow-up period.

Baseline pain scores were obtained after physical examination using the 0-10 Numeric Pain Rating Scale (NPRS). Patient demographic characteristics were also collected at this time. A second pain score and data on treatment regimens used in the ED and any new outpatient prescriptions were obtained at time of discharge. Follow-up pain scores were then obtained at 12-, 24-, 48-, and 72-h intervals thereafter. For follow-up pain scores, telephone calls were made by study coordinators as close as possible to 12, 24, 48, and 72 h after discharge. If the follow-up phone calls were made beyond the 12-, 24-, 48-, and 72-h timeframe, patients were requested to recall their pain scores at the approximate time. During these calls, information was collected about further medical or dental care, analgesic use, and the occurrence of adverse effects. All patients were offered to have a \$10 gift card sent to their home at time of the completion of

Statistical Anaysis

We considered a 2-point difference in the 11-point NPRS to be clinically meaningful (19). Assuming a standard deviation (SD) of 3, power of 80%, and two-sided alpha of .05, we estimated a sample size of 37 patients per treatment group would be necessary to detect this difference. Statistical analysis was performed using Stata software, version 16.0 (College Station, TX). A two-tailed alpha of .05 was used as the threshold of significance for all statistical testing. Chi-square testing was performed for continuous, parametric data and Wilcoxon-rank sum testing was used for categorical and nonparametric data.

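### Entry sets no minimum baseline NPRS, so patients with little room to improve can be randomised; how much power this costs depends on their unknown share and on not adjusting for baseline

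*Combined protocol and SAP*

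**What the plan says.** Under Materials and Methods, adults who come to one of two emergency departments with dental pain are screened, and those with a clinical diagnosis of pulpitis or apical abscess may enter. The diagnosis is clinical: "Diagnosis was made based on physical examination revealing pain with percussion of the affected tooth or teeth", with or without visible gingival signs. The exclusions contain one pain-severity item, at the upper end (hospitalisation for intractable vomiting or pain). There is none at the lower end.

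The 0-10 NPRS is recorded after the examination, as the baseline measurement. It is not described as a condition of entry, and its timing relative to randomisation is not given.

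The statistical section sizes the trial on this scale: "We considered a 2-point difference in the 11-point NPRS to be clinically meaningful". It continues: "Assuming a standard deviation (SD) of 3, power of 80%, and two-sided alpha of .05", and concludes that "we estimated a sample size of 37 patients per treatment group would be necessary to detect this difference". The named tests are chi-square and Wilcoxon rank-sum. No analysis adjusted for baseline score is planned. The title gives the outcome as time to pain resolution, but resolution is not defined.

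**The concern.** The entry finding is evoked pain; the outcome is a self-reported score. A tooth can be tender to percussion in a patient whose reported score is low, and nothing in the eligibility text excludes that patient. The scale stops at 0, so someone who starts low has little room to show a benefit, and someone who scores 0 already meets any plausible definition of resolution.

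Such patients affect an unadjusted comparison in two ways. They pull the mean difference below the 2 points the trial was sized for, and they widen the spread of follow-up scores because they sit well below everyone else. Either reduces power, and the design has under one percentage point to spare. At stake is how to read a null result: the drug may not work, or part of the sample may have had little pain to lose.

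**Working it through.** **Inputs from the statistical section.** Difference 2, SD 3, two-sided alpha .05, power 80%, 37 per group. Allocation is about 1:1 (blocks of four). The share f of low-baseline patients is not in the documents, so every value of f below is an assumption.

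**The plan's figure.** The normal approximation gives n = 2 × [3 × (1.960 + 0.842) / 2]² = 35.3, so 36 per group. The two-sample t-test gives 36.3, so 37, which matches the plan. At 37 per group the noncentrality is (2/3) × √(37/2) = 2.867 on 72 degrees of freedom, and power is 80.8%.

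**Calculation 1: low-baseline patients show no effect.** The mean difference becomes 2 × (1 − f), with SD held at 3.

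| f (assumed) | Difference | Noncentrality | Power at 37 per group | n per group for 80% |
|---|---|---|---|---|
| 0 | 2.0 | 2.867 | 80.8% | 37 |
| 5% | 1.9 | 2.724 | 76.7% | 41 |
| 10% | 1.8 | 2.581 | 72.1% | 45 |
| 20% | 1.6 | 2.294 | 61.9% | 57 |

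A variant places those patients at 0 in both arms and gives the rest SD 3 and an assumed control mean of 4 to 6. Power is then 73-77% at f = 5%, 66-72% at 10% and 52-63% at 20%.

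**Calculation 2: simulation on the bounded scale.** All settings are assumptions. Baselines are spread evenly over 5-10, except a share f spread evenly over 0-2. Follow-up is 0.8 × baseline + N(0, 2.4), minus 2 if treated, rounded and clipped to 0-10. There are 37 per group and 20,000 trials. The unadjusted test is a t-test; the adjusted one is a linear model with baseline as covariate.

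| f (assumed) | Mean difference | Control SD | Unadjusted power | Baseline-adjusted power |
|---|---|---|---|---|
| 0 | 1.85 | 2.6 | 86% | 93% |
| 10% | 1.76 | 2.8 | 77% | 92% |
| 20% | 1.67 | 3.0 | 68% | 91% |

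Three things follow.

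- Low-baseline patients still show part of the effect, about 0.7 points at baseline 0, 0.9 at 1 and 1.2 at 2, because pain in controls can rise. Calculation 1 is therefore the pessimistic case for dilution.
- From f = 0 to 20% the mean difference falls by about 10% (0.18 / 1.85), while the control SD rises by about 15% (0.4 / 2.6). Much of the unadjusted loss is extra spread, which adjustment removes.
- At f = 0 the simulated SD is 2.6, below the planned 3. The drop in power down the column is informative; its absolute level is not.

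The two calculations lose similar amounts of unadjusted power, but for partly different reasons, so they should not be counted as two confirmations of one mechanism.

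**The case against.** The strongest case against is that nothing here is an error. The 37 reproduces. Screening is limited to people who came to an emergency department with dental pain, so very low scores should be uncommon. The 2 points and SD 3 may already describe an unselected population, since the documents do not tie them to patients with high baseline pain. Enrolling everyone with the diagnosis is a legitimate pragmatic choice. All of this stands, and it keeps the point conditional on f.

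A reader might infer that any patient scoring 0-2 can show neither a 2-point benefit nor resolution. The scale does not support that. Only a patient at 0 has no resolution left to show; one at 1 can resolve, and one at 2 can both resolve and fall by 2. In addition, the 2 points in the plan is a difference between groups, not a response threshold for each patient.

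A reader might also infer that baseline adjustment cannot help, because the floor has removed the effect. The simulation contradicts this: adjusted power stays at 91-93% across the range. The size of that gain depends on the assumed link between baseline and follow-up, but the direction is what one expects when extra spread drives much of the loss.

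Finally, recruitment ran from September 2017 to May 2019 and the document is dated 12/01/2020, so an entry criterion cannot reach these patients. Restricting the analysis does not restore power either. With the full 2 points and SD 3, 37 × 0.9 ≈ 33 per group gives 76%, and 37 × 0.8 ≈ 30 gives 72%. That also stands, and it shapes the fix.

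**Conclusion.** The point holds as a design weakness of limited and unknown size. No minimum NPRS is required for entry, no baseline distribution is assumed, and the stated tests ignore baseline, in a trial with 80.8% power on its own assumptions. If low-baseline patients showed no effect and SD stayed at 3, power would be about 77%, 72% and 62% at shares of 5%, 10% and 20%. If they showed a partial effect, the simulation loses about 9 points of unadjusted power at 10% and 18 at 20%, most of it recoverable by adjustment. If no one was near the floor, nothing is lost.

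The documents do not support the conclusion that the trial was underpowered or that the sample size is wrong: the share f is not given and is probably small in this setting.

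**What to change.** **Further enrolment or a repeat trial.** Add one inclusion criterion: a minimum baseline NPRS, scored before randomisation and set clearly above the 2-point target. A score of 4 is one example with no source in the documents; the trial team should choose and justify the level. State the baseline distribution behind the 2 points and SD 3, and make the baseline-adjusted follow-up score part of the planned analysis.

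**Patients already randomised.**

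- Keep everyone in the main analysis.
- Report the baseline NPRS distribution by arm, including how many fall below the chosen cut. This alone may settle the question.
- Adjust the follow-up score for baseline, and say that the stated plan did not include this.
- Label any analysis restricted to patients above the cut as a post hoc sensitivity analysis.
- Confirm that baseline NPRS was recorded before randomisation. Both the adjustment and the restriction depend on it.

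**Cost.** One line of eligibility text, and one or two extra analyses of a score already collected. The downside of the criterion is a slightly smaller eligible pool and a conclusion limited to patients with more than minimal pain.

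### Patients who need extraction or pulpectomy within 72 h leave the study, and the plan does not say how they are analysed, so later pain comparisons appear to cover only patients without a procedure

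*Combined protocol and SAP*

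**What the plan says.** Patients are randomised at enrolment in the emergency department. A pain score on the 0-10 scale is taken at baseline and again at discharge. After that: "Follow-up pain scores were then obtained at 12-, 24-, 48-, and 72-h intervals thereafter". Within this window the methods state: "Termination from study enrollment occurred if the patient required dental extraction or pulpectomy during the 72-h follow-up period". On the telephone calls the plan says: "During these calls, information was collected about further medical or dental care, analgesic use, and the occurrence of adverse effects".

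The Statistical Analysis section gives a sample size based on a 2-point difference and SD 3, the software, the alpha level, and one sentence on methods: "Chi-square testing was performed for continuous, parametric data and Wilcoxon-rank sum testing was used for categorical and nonparametric data". It mentions no analysis population, intention-to-treat rule, handling of missing scores or sensitivity analysis. It does not say how a patient whose participation ended with a procedure is counted.

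**The concern.** The event that ends participation happens after randomisation and inside the 12-72 h outcome window, and it is plausibly related to pain, which is the outcome. If no score follows the procedure, a two-group test at 48 or 72 h uses only patients who did not need one. If treatment affects pain, and pain affects who needs a procedure, the patients left in the two arms are no longer comparable as randomised.

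The restriction builds up over time. A patient treated at 40 h still contributes 12 h and 24 h scores to tests at those times. A separate test at 48 h or 72 h, however, has no means of using those earlier scores.

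Ending observation at a procedure can be defended if the question is pain in the absence of dental intervention. The plan states neither that question nor an analysis that answers it. The title refers to time to pain resolution, and there too the plan does not say whether a patient who had a procedure counts as resolved, unresolved or censored.

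**Working it through.** **1. The plan's own figure.** Inputs from Statistical Analysis: difference 2, SD 3, power 80%, two-sided alpha 0.05. For a two-sample t-test the standardised difference is 2/3. This requires 36.3 per group, rounded up to 37, with power 0.808. The stated result ("we estimated a sample size of 37 patients per treatment group would be necessary to detect this difference") is therefore reproduced.

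**2. A yardstick.** The 95% confidence interval half-width with 37 per group is t(0.975, 72) × SD × √(2/37) = 1.993 × 3 × 0.2325 = 1.39 points.

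**3. Bias from pain-driven loss at one time point.** The documents give no procedure rate, so every loss rate here is an assumption. Placebo scores are drawn from N(6, 3) and active scores from N(4, 3). The probability p(Y) that a patient with score Y leaves follows logit p(Y) = a + b(Y − 5), the same in both arms. The mean among remaining patients is E[Y(1 − p(Y))] / E[1 − p(Y)], and the bias is the difference in these means minus the true difference.

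Unbounded normal scores put 11.4% of each arm outside 0-10, so scores are rounded and clipped to the scale. The true difference then becomes 1.80 and the SD 2.72, and the half-width becomes 1.993 × 2.72 × 0.2325 = 1.26.

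| a, b | Loss, placebo/active (0-10 scale) | Bias, 0-10 scale | Bias, unbounded scores | 0-10 bias ÷ 1.39 |
|---|---|---|---|---|
| −3, 0.3 | about 8%/5% | −0.04 | −0.09 | 3% |
| −2, 0.3 | about 18%/12% | −0.09 | −0.16 | 6% |
| −2, 0.5 | about 24%/14% | −0.24 | −0.36 | 17% |

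The unbounded version overstates the bias, roughly twofold at the lowest rate. Even there, coverage of the 95% interval stays at 95% up to 19%/12% and falls to 92% at 25%/14%. With no true effect and the same leaving rule in both arms, the difference stays at about 0.

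**4. Bias in the other direction.** The effect is inflated only if active patients are more likely to have a procedure at the same pain score. Adding 1 or 2 to the active log-odds means odds ratios of e¹ = 2.7 and e² = 7.4.
- Odds ratio 7.4: about +0.23 with unbounded scores (7%/14% loss) and +0.29 on the 0-10 scale.
- Odds ratio 2.7, no true effect: a spurious difference of about 0.29 at 10%/19% loss, with a t-test rejection rate of 6.9% against a nominal 5%.

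**5. Would a repeated-measures model help?** Scores at 12, 24, 48 and 72 h were simulated with SD 3, correlation 0.6 and a constant difference of 2, with a procedure possible in each interval between calls. Estimates at 72 h:

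| Loss depends on | Setting | Model | Remaining patients only |
|---|---|---|---|
| Last recorded score | lower loss, 10%/6% | 2.00 | 1.94 |
| Last recorded score | higher loss, 33%/17% | 2.00 | 1.68 |
| Pain not yet recorded | lower-loss setting | 1.97 | 1.92 |
| Pain not yet recorded | higher-loss setting | 1.81 | 1.61 |

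When recorded scores explain who leaves, the model removes the bias. When they do not, about half remains: 2.00 − 1.81 = 0.19 against 2.00 − 1.61 = 0.39 in the last row. These runs used unbounded normal scores and no baseline score, so they show the principle rather than the exact performance of the model proposed below.

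**The case against.** **The text ends enrolment; it does not exclude anyone from analysis.** This stands as a limit on what can be claimed. The document does not say that scores were discarded or never sought after a procedure. But no later score is described, and no rule for terminated patients is given, so loss of later scores remains the natural reading.

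**Materiality is not shown.** This largely stands. Up to about 18%/12% loss the shift is under a tenth of a point, and nothing in the document supports rates of 24%/14% or more within 72 h. It does not remove the point, because without counts by arm a reader cannot tell which case applies.

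**Stronger readings.** A reader might infer that the rule inflates the treatment effect or the type I error. The document does not support this. It would require active patients to have procedures more often at equal pain, with an odds ratio of at least 2.7 in the scenarios tried. Patients, treating providers and investigators were blinded, and no mechanism is offered. A reader might also infer that terminated patients were removed from every time point, or that the trial fell short of 37 per group. The first is not stated, and the second cannot be shown because the number enrolled is not given.

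**The remedy may be a matter of preference.** This is fair for a worst-rank analysis that counts a procedure as the worst outcome. In simulation its rank-sum power against dropping these patients was 70% v 60% at 25%/14%, but 52% v 87% at 7%/14% and 59% v 74% when 10% per arm left for reasons unrelated to pain. It is less fair for the repeated-measures analysis, which simply uses scores already collected.

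**Conclusion.** The concern holds in a limited form. The plan ends participation after randomisation for an event plausibly tied to the outcome and gives no way to handle the affected patients. Following it as written can bias comparisons after a procedure. Time points before the procedure are sound.

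The size and direction in this trial are unknown. If loss is driven by pain through the same rule in both arms, the true difference is diluted by about 0.04 to 0.24 points over the assumed losses of 8%/5% to 24%/14%, against a half-width of about 1.4 (1.26 with the clipped SD). That is negligible if procedures were few and balanced, and worth correcting if they were common or unbalanced. These figures rest on the assumed score distributions and leaving rule.

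The analysis and reporting should be amended. Nothing here bears on when a patient should have a dental procedure.

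**What to change.** - **Analysis.** Keep all patients in their randomised groups. Analyse every score collected up to the procedure in a repeated-measures model across 12, 24, 48 and 72 h, adjusted for the baseline score, with confidence intervals for the difference at each time. State that the model estimates pain as if no procedure had occurred.
- **Reporting.** Give the number of procedures and of unreached calls by arm and by interval between calls. The calls asked about further dental care, but exact procedure dates may not have been recorded, so the interval is the finest timing that can be assumed.
- **Optional.** A worst-rank analysis may be added if it is labelled as answering a different, composite question and its possible loss of power is acknowledged.
- **Later studies.** Continue collecting the scheduled scores after a procedure.

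**Cost.** Low: one table and one model on data already collected. There are two drawbacks. The model removes the bias fully only if recorded scores explain who leaves; otherwise about half may remain. Enrolment ran to May 2019 and the analysis is described in the past tense, so the work must be labelled post hoc if the data have been seen, and it then carries less weight than a prespecified analysis.

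### The 37 per group is a zero-loss t-test figure, and the tests the plan names leave the baseline pain score unused

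*Combined protocol and SAP*

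**What the plan says.** The sample-size statement is in the Statistical Analysis section at the end of the combined document. It sets the target effect ("We considered a 2-point difference in the 11-point NPRS to be clinically meaningful") and the other inputs ("Assuming a standard deviation (SD) of 3, power of 80%, and two-sided alpha of .05"), and then concludes: "we estimated a sample size of 37 patients per treatment group would be necessary to detect this difference". It does not name the test, the time point or any allowance for missing scores, and it gives no enrolment target separate from the 37.

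The same section describes the analysis: "Chi-square testing was performed for continuous, parametric data and Wilcoxon-rank sum testing was used for categorical and nonparametric data". A t-test appears nowhere, and neither does an analysis adjusted for baseline.

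The Materials and Methods text describes two routes by which a score can be lost. One is a removal rule: "Termination from study enrollment occurred if the patient required dental extraction or pulpectomy during the 72-h follow-up period". The other is that the scores at 12, 24, 48 and 72 h come from telephone calls after discharge. A baseline NPRS is taken in the ED from each patient, and a second score is taken at discharge.

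**The concern.** A sample-size figure supports its stated power only if the analysis is the one assumed and the assumed number of patients contribute data. Both links are loose here. The calculation matches a t-test that the analysis text does not mention. It also matches complete follow-up, in a design that has a removal rule and depends on reaching ED patients by telephone over three days.

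At stake is how the 80% should be read. If some of the 37 have no score at the time point compared, the chance of missing a true 2-point difference is larger than the 20% the plan implies. In addition, an unadjusted comparison does not use the baseline pain score, which costs nothing further to include and can recover some or all of that power.

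**Working it through.** **Inputs from the Statistical Analysis section:** difference δ = 2, SD σ = 3, two-sided alpha .05, power 80%, 37 per group. Equal allocation follows from the blocks of four in Materials and Methods. The loss rates and baseline correlations used below are assumptions, because the documents give neither.

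**1. Reproducing the 37.** The normal approximation gives n = 2(1.960 + 0.842)² × 3²/2² = 35.3, so 36 per group. The exact two-sample t-test uses a noncentral t with 2n − 2 degrees of freedom and noncentrality (δ/σ)√(n/2). At n = 37 the noncentrality is (2/3)√18.5 = 2.867 and the critical value on 72 df is 1.993, which gives power 80.8%. At n = 36 power is 79.7%. The exact solution is 36.3, rounded up to 37. The plan's figure is therefore correct for a t-test with every patient scored, and it has no margin: one fewer scored patient per arm takes t-test power just under 80%.

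**2. Changing only the test.** Chi-square does not compare NPRS levels as continuous data, so among the named tests the rank-sum is the one that fits. Its efficiency relative to the t-test for normal data is 3/π = 0.955, so 37 patients act like 37 × 0.955 = 35.3, and power is 78.9%. Simulation with normal data gave 79.1%. Simulation with rounded, bounded 0–10 scores matched to a difference of 2 and SD 3 gave 79.6% to 80.2%. Without that matching, clipped scores gave about 78%. The change of test alone therefore costs about 0 to 2 points. Restoring the full t-test figure would take 37/0.955 = 38.7, or 39 per group.

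**3. Adding loss, if 37 is the number enrolled.** Scored patients per arm are 37(1 − loss). The rank-sum column multiplies that number by 0.955.

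| Assumed loss | Scored per arm | t-test | Rank-sum |
|---|---|---|---|
| 0% | 37 | 80.8% | 78.9% |
| 5% | 35.2 | 78.7% | 76.8% |
| 10% | 33.3 | 76.4% | 74.4% |
| 20% | 29.6 | 71.3% | 69.2% |

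Rank-sum simulations agree: 73.6% to 75.1% at 33 per arm, and 69.5% to 70.3% at 30. For scale, keeping 37 scored would have required enrolling 37/0.9 = 41.1, so 42 per group, at 10% loss, and 37/0.8 = 46.3, so 47, at 20%.

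**4. Using baseline NPRS.** ANCOVA on arm and baseline reduces the residual SD to σ√(1 − r²), where r is the correlation between baseline and follow-up scores. At r = 0.3 the SD is 3√0.91 = 2.86. At r = 0.5 it is 3√0.75 = 2.60. Power from the same noncentral-t formula is:

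| Assumed r | No loss (37) | 20% loss (29.6) |
|---|---|---|
| 0.3 | 84% | 75% |
| 0.5 | 90% | 83% |

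The one degree of freedom spent on the covariate changes these by less than 0.1 point.

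**The case against.** The strongest reply is that nothing has been miscalculated. The 37 follows exactly from the stated inputs, and the sentence can fairly be read as the number needed for analysis rather than the number enrolled. On that reading the t-test power stands, and the gap is only that no enrolment target is given. This is correct, and the documents do not settle which reading is meant.

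The reply can add that the design limits loss. Patients without a telephone number are excluded, late calls may collect recalled scores, and a gift card is offered. A comparison at discharge would not depend on the telephone at all. These points stand, and they are why the loss rates above are only a range. They do not show that loss is zero, and the removal rule operates however well the calls go.

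The sentence naming the tests also looks garbled, with data types attached to the wrong tests, so it is weak evidence of a firm choice of rank-sum for NPRS. Little depends on this, because the change of test costs at most about 2 points.

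Two stronger conclusions are tempting. A reader might infer that the design falls clearly below 80%. The documents do not support that, because the rank-sum shortfall is small and the larger shortfalls rest on assumed loss rates and on reading 37 as enrolled. A reader might also infer that the trial relies on 80% power to treat a null result as excluding a 2-point difference. The documents contain no rule or statement on how a null result would be read.

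Finally, Materials and Methods reports the study as carried out from September 2017 to May 2019, and the document is dated 12/01/2020. Naming a new primary analysis at that stage could be a change made after the data were seen. This objection stands and shapes the fix.

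**Conclusion.** The point holds in a limited form. The 37 per group is the two-sample t-test number for complete data and carries no allowance for loss, while the analysis text names no t-test and the design provides for patients leaving and for scores by telephone. The mismatch of test is minor, at about 79% instead of 80.8%. Loss is the material part, but its size is unknown. If 37 means enrolled, power is about 74% to 76% at an assumed 10% loss and 69% to 71% at 20%, depending on the test. If 37 means scored at the time point analysed, the t-test power stands.

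An unadjusted comparison also gives up precision that the trial has already collected. The size of the ANCOVA gain rests on the assumed correlation. At 0.5 it keeps power above 80% even with 20% loss (83%); at 0.3 it does not (75%).

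**What to change.** 1. Analyse follow-up NPRS by ANCOVA on treatment arm and baseline NPRS, in place of an unadjusted test. If this was not fixed before unblinding, label it post hoc or supportive and also report the comparison that was originally intended.
2. Qualify the power statement: the 80% applies to a two-sample t-test with 37 patients per group scored at the time point analysed. Name that time point and the test, and say whether 37 was an enrolled or an evaluable number.
3. Report the number scored per arm at each time point, so that a reader can see how far the data fell from 37.

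This costs a few sentences of analysis text, one count per arm and time point, and one regression on data already held. It needs no extra patients. ANCOVA recovers precision only; it does not address whether patients without a score differ from those with one.

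### The available text names no primary outcome: time to pain resolution is undefined, the 2-point NPRS difference is tied to no time, and .05 governs every test

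*Combined protocol and SAP*

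**What the plan says.** The cover page titles the study "The Effects of Dexamethasone on the Time to Pain Resolution in Dental Periapical Abscess". Nothing in Materials and Methods or the statistical section says what counts as resolution, how a patient unresolved at 72 h is treated, or how time to resolution is compared.

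Pain is measured on the 0-10 NPRS at baseline and five times afterwards. At the ED visit, "A second pain score and data on treatment regimens used in the ED and any new outpatient prescriptions were obtained at time of discharge"; then, "Follow-up pain scores were then obtained at 12-, 24-, 48-, and 72-h intervals thereafter".

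The statistical section sizes the trial for a 2-point NPRS difference with SD 3, 80% power and two-sided alpha .05, giving 37 per group. It names no time for that difference and does not say whether it is a raw score or a change from baseline. On error control it says only: "A two-tailed alpha of .05 was used as the threshold of significance for all statistical testing". The tests named are chi-square and Wilcoxon rank-sum.

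On early exit: "Termination from study enrollment occurred if the patient required dental extraction or pulpectomy during the 72-h follow-up period". How later missing scores are handled is not stated.

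The study was "undertaken at two academic medical center EDs between September 2017 and May 2019"; the cover page reads "Document. Date: 12/01/2020".

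**The concern.** Three parts of the document should point to the same comparison and do not. The title points to an event time, the sample size to a difference in mean pain score at an unnamed time, and the testing rule to everything at once. No outcome is called primary.

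Two things are at stake. First, with five eligible scores and one threshold for all of them, nothing in the text prevents whichever time reaches .05 from being presented as the result. Second, the tests listed do not estimate time to resolution with censoring at 72 h. If no event was fixed earlier, a claim about time to resolution would rest on a definition chosen after enrolment closed.

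Termination for extraction or pulpectomy adds to this. Those losses may be related to pain, so the way missing scores are handled can change the answer at the later times.

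**Working it through.** **Inputs.** From the statistical section: difference 2, SD 3, two-sided alpha .05, power 80%, 37 per group. From Materials and Methods: four telephone scores plus discharge, and roughly equal groups (blocks of four). Assumed, because the documents give none: the correlation ρ between scores, taken as 0.5 to 0.9 for error rates and 0.5 to 0.8 for power.

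**1. The plan's own figure.** Normal approximation: n = 2(1.960 + 0.842)² × 3² / 2² = 35.3, so 36 per group. The two-sample t-test gives 36.3, so 37, which matches. Power at 37 is 80.8%; at 36 it is 79.7%. With Wilcoxon, the rank test the text lists, simulation on normal data gives about 79%. So 37 fits one comparison of means at one time.

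**2. Missing scores.** The text does not say whether 37 means enrolled or with a score. If enrolled, and 2, 4 or 7 per group lack the score, t-test power is 78.5%, 76.0% or 71.9%.

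**3. False-positive rate if each time is tested at .05 and any one may count.** For k equally correlated statistics,

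rate = 1 − ∫ φ(u) [Φ((1.96 − √ρ u)/√(1−ρ)) − Φ((−1.96 − √ρ u)/√(1−ρ))]^k du.

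| ρ | four follow-up times | five, with discharge |
|---|---|---|
| 0 (1 − 0.95^k) | 18.5% | 22.6% |
| 0.5 | 15.6% | 18.3% |
| 0.7 | 13.0% | 14.8% |
| 0.8 | 11.4% | 12.7% |
| 0.9 | 9.4% | 10.2% |

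If correlation instead decays over time (lag-one 0.9 to 0.5), the rates are 10.3-16.6% for four times and 11.8-20.2% for five. If one time was fixed beforehand, the rate is 5%.

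**4. Power of Holm with the same patients.** Holm rejects at least one time when the smallest p-value is at or below .05/k, which is .01 for five times. Simulated t-tests, 37 complete patients per group, SD 3, ρ = 0.5, 0.7, 0.8:
- 2 points at all five times: 89.6%, 83.2%, 78.9%.
- 2 points at two of the five: 76.4%, 72.8%, 70.2%.
- For any single time with a 2-point effect, power at alpha .01 is 58.9%.

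**5. Holm against a prespecified average over 12-72 h.** SD of the mean of four scores = 3√((1 + 3ρ)/4) = 2.37, 2.64, 2.77. With 2 points at all four times, the average has power 94.7%, 89.5%, 86.6%, and Holm over four has 88.8%, 83.1%, 79.5%. The differences are 5.9, 6.4 and 7.1 points. With 2 points at only two of the four (mean difference 1), the average falls to 43.2%, 36.2%, 33.5%, against 79.1%, 75.2%, 73.1% for Holm.

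**6. The titled outcome.** Under proportional hazards, the hazard ratio detectable with 80% power is exp((1.960 + 0.842)/√(events/4)). That is 1.92 if all 74 patients resolve by 72 h and 2.51 if 37 do. These resolution rates are assumed, and the figures show only that the sample size was not built on this outcome.

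**The case against.** The strongest objection is that text may have been lost. In Materials and Methods, the sentence on the participants' gift card stops midway, directly before the statistical section, and an outcome statement could have followed. This stands as a limit: the point can be made only for the text as available. The statistical section that follows still ties the 2 points to no time.

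Second, the false-positive rate is contingent. A reader might infer that the trial's error rate is inflated. The documents do not support that, because they nowhere say that every time was tested or that any one would count. What they show is an unidentified primary comparison.

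Third, a reader might infer from the dates that the primary was chosen after the results were seen. The documents do not show this either. They do not say when data were unblinded, and a protocol approved before enrolment may have fixed a primary.

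Fourth, the sentence listing the tests is visibly garbled (it assigns chi-square to continuous data and Wilcoxon to categorical data), so it is weak evidence that no other method was used. The t-test powers above are also for a test the text does not list, though for normal data Wilcoxon costs only about 2 points. They would not carry over to a worst-rank analysis.

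None of this supplies a stated primary, a resolution event or a rule for missing scores.

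**Conclusion.** The point holds for the available text. No primary outcome is named, the titled outcome is undefined, the 2-point difference belongs to none of the five scores, and .05 applies throughout without order. It would be wrong to read this as an error in the sample size: 37 per group is right for one comparison of means.

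The size of the harm depends on facts not in the document. It is nil for a time fixed beforehand. If any time may count, the rate is roughly two to nearly four times the nominal 5%, given the assumed correlations. This must be fixed because it decides what the trial's conclusion rests on. Confidence is moderate, given the broken sentence and a possible earlier protocol.

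**What to change.** 1. **If a protocol fixed before the data were seen names a primary NPRS time**, state it, test only that at .05, and report the other times as estimates with 95% CIs and no significance claim.
2. **If none was fixed**, do not choose a time or an average now and test it at .05; a post hoc label discloses the selection but does not control error. Use Holm across all five post-baseline times, or report all five as estimates with CIs and no significance claim. Label the analysis as not prespecified.
3. **Missing scores.** Analyse all randomised patients and keep scores collected before termination. Report terminations for extraction or pulpectomy by group and time; the follow-up calls are a source, since "During these calls, information was collected about further medical or dental care, analgesic use, and the occurrence of adverse effects". State one method for later missing scores, with a sensitivity analysis. Worst rank (pain or needing a procedure) and multiple imputation (pain had no procedure occurred) are examples that answer different questions.
4. **Title outcome.** Either define resolution (an NPRS threshold, and whether it must be sustained) and analyse it by an interval-censored or discrete-time method, labelled as not the basis of the sample size, or restate the question as pain intensity over 72 h.

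The cost is SAP wording and a modest re-analysis of collected data, with no new patients. Prespecification cannot be restored if nothing was fixed earlier. An isolated time with p below .05 can no longer carry the conclusion. Holm costs about 6-7 points of power against a prespecified 12-72 h average if the effect lasts (four times).
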